### 4.3 Intervention

Participants will be randomised to administration of either active tablets containing metformin or an identical placebo. Once they have been recruited they will start by taking one tablet twice a day. If they have no side effects after 24 to 48 hours they will increase to 2 tablets twice a day. If again they experience no side effects after 24 to 48 hours they will increase to 3 tablets twice a day. If they are not tolerating the tablets the dose can also be decreased. The maximum dose of metformin will be 1.5mg in the morning and evening. Treatment will continue until delivery. The study will not alter or interfere with any treatment or care given routinely to women with early onset pre-eclampsia.

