17. Description of any planned adjustment for multiplicity, and if so, including how the type 1 error is to be controlled

No adjustment for multiplicity will be performed. The strategy for outcome testing is pre-specified and maintains the overall trial error rate at 0.05.

18. Confidence intervals (CI) to be reported

Standard 95% confidence intervals will be used to present analysis of the primary adjusted outcome. For secondary outcomes it is planned to the adjusted width of CI used.³

19. Adherence and Protocol Deviations

Adherence:

Trial medication will be administered to mothers on an inpatient basis. Measures to monitor adherence are: The trial medication will be written up on the treatment chart and the chart will be signed by the nursing staff to confirm that the participant has taken the medication and to confirm compliance. The research midwife will monitor the treatment chart to assure compliance. The dosing schedule details a programmed escalation of dose in the of side effects. We will use two measures of dosing in the metformin arm: (i) average daily dose of tablets = number of ingested medications/days of therapy and (ii) percentage of maximum dose = ingested medications/ total maximum medications.

Description of how adherence to the intervention will be presented:

Adherence will be presented on the two measures detailed above, using descriptive statistics (N, mean, SD, median, minimum, maximum) converted to metformin dose for the intervention arm.

Definition of protocol deviation for the trial and description in trial results:

Protocol deviations due to errors in applying inclusion/exclusion criteria, the wrong intervention being administered will be documented in trial results either in patient flow diagram or text. The primary outcome will not be subject to ascertainment error due to its unambiguous nature. Prior to unblinding of treatment all protocol deviations will be assessed, and determination made about inclusion of these participants within the trial analysis populations. Determinations will be presented in the research results in the patient flow diagram and possibly in the text.

³ Ludbrook J. Multiple inferences using confidence intervals. Clin Exp Pharmacol Physiol 2000;27:212 - 215.

19. Analysis populations.

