The intention-to-treat population will include all randomized patients, regardless of their eligibility, according to the treatment they were randomized to receive. Primary outcome will also be tested on trial arms based upon treatment received as a sensitivity analysis.

[figure not shown]
Section E: Trial Population

20. Screening Data

Screening data will be collected and reported. The name of patients assessed for eligibility and the reason for not enrolling will be recorded and reported. The trial inclusion and exclusion criteria are specified in the protocol. A CONSORT diagram will be used to summarize and present this data.

21. CONSORT flow diagram template for the PI2 trial

The following CONSORT flow diagram will be used to detail enrollment, randomization, treatment allocation, reasons for not receiving treatment, follow up and analysis

22. Baseline characteristics

List of Baseline characteristic to be summarized by treatment groups and presented in tables:

- Gestational age at randomization
- Maternal age in years
- BMI
- Ethnicity (black, colored, other)

- Smoking
- Aspirin usage
- Calcium usage
- HIV status
- Chronic hypertension
- Parity (Nulliparity; Multiparity +/- hypertension in previous pregnancy)
- New paternal parity in current pregnancy
- Pre-randomization highest systolic and diastolic blood pressure
- 24 hour Creatinine ratio
- Haemoglobin, platelet count, urea and creatinine before randomization
- Estimated fetal weight on ultrasound
- Presence of absent flow on umbilical artery doppler.

Details of how baseline characteristics will be descriptively summarized:

Categorical data will be summarized by numbers and percentages. Continuous data will be summarized by mean, SD and range if data are normal and median, IQR and range if data are skewed. Minimum and maximum values will also be presented for continuous data. Tests of statistical significance will not be undertaken for baseline characteristics; rather the clinical importance of any imbalance will be noted.

Section F: Analysis

23. Outcome definitions

Primary outcome definition:

The primary outcome is time from randomization until delivery, measured in hours and presented in days. The summary of interest is median prolongation and data will not be transformed prior to analysis. If a fetus does demise during expectant management, we will give it a length of pregnancy prolongation of zero and will include it in the primary analysis.

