Adjustment for covariates for each primary and secondary outcomes:

Primary outcome: A covariate adjusted analysis with both treatment group and gestational age design-based strata modelled as fixed will constitute the primary analysis outcome. Unadjusted and adjusted CPH analysis are only supplemental to this primary analysis.

Secondary outcomes: Composite binary outcomes will be modelled using a logistic regression model containing both treatment group and gestation aged based strata.

Methods used for assumptions to be checked for statistical methods:

Quantile regression makes no distributional assumptions (assessed using residuals) apart from assuming the outcome is continuous. Secondary outcomes tested using exact logistic regression or Fisher's exact test make no distributional assumptions.

Sensitivity analyses:

Sensitivity analysis will be conducted on the primary outcome are:

- (i) Treatment received Analysis will be adjusted by median quantile regression as already specified for the primary outcome intention to treat analysis. Treatment received, given varying dosage schedule is defined as an average daily dose.
- (ii) Gestational age as an effect modifier. An interaction between treatment and gestational age strata will be using the same model as the primary outcome. Given study size it is acknowledged that this has low power to detect an interaction effect.
- (iii) Covariate adjusted. The trial investigators consider that a mother with absent UAD flow, an estimated fetal weight less than the 10th centile and an estimated fetal weight less than the 3rd centile are more likely to

be associated with shorter randomization to delivery times. Covariate adjustment for these factors may increase the precision of the primary outcome measure if there is a correlation between them and delivery time.

(iv) Survival analysis. Will be performed using Cox proportional hazards regression (CPH) adjusted for gestational age strata and Kaplan-Meier survivorship curves.

No sensitivity analysis for primary outcome outcomes is planned for missing data as we expect these mothers not to have missing outcome data or baseline measured pretreatment covariates. If the neonate is lost to follow-up the outcome will be set to missing, a sensitivity analysis will be performed to assess strength of inference given pattern of missingness by setting missing values to no event, mean event rate or event to assess dependence on inference on the unknown outcomes.

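### The treatment-received sensitivity analysis uses average daily dose as its exposure, and under the Protocol 4.3 step-up that average depends on time to delivery, which is the outcome

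*SAP*

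**What the plan says.** SAP section 24, Sensitivity analyses, item (i), gives the method: "Analysis will be adjusted by median quantile regression as already specified for the primary outcome intention to treat analysis". It then fixes the exposure: "Treatment received, given varying dosage schedule is defined as an average daily dose". The formula stands in SAP section 19, Adherence and Protocol Deviations: "average daily dose of tablets = number of ingested medications/days of therapy". SAP section 23 defines the outcome: "The primary outcome is time from randomization until delivery, measured in hours and presented in days". Protocol 4.3 sets the end of therapy: "Treatment will continue until delivery".

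The documents describe dosing in two ways. Protocol 4.3 has a step-up: "Once they have been recruited they will start by taking one tablet twice a day". After 24 to 48 hours without side effects this becomes two tablets twice daily, and then "If again they experience no side effects after 24 to 48 hours they will increase to 3 tablets twice a day". Decreases are allowed for intolerance. SAP section 19 also speaks of a planned escalation, in a sentence with words missing. Protocol 7.2.5 instead starts every participant on six tablets a day, reduces for side effects, and allows a return to six.

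The analysis is also described in two ways. The other SAP section numbered 19, Analysis populations, says: "Primary outcome will also be tested on trial arms based upon treatment received as a sensitivity analysis". Protocol 8.6 lists treatment received first among the sensitivity analyses but does not define it.

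**The concern.** An exposure in a regression should be fixed before the outcome, or at least not be calculated from it. Here the denominator of the exposure is, apart from any delay in starting or early stopping, the outcome itself. If dose climbs over the first days, a woman who delivers early has spent most of her treatment on the low steps and has a low average. A woman who delivers late has spent most of it on the top step and has a high average. Dose and prolongation are then associated whether or not the drug works.

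A sensitivity analysis is meant to show whether the main result is robust. One that tends to show benefit under the null cannot do that, and readers could take it as corroboration. The plan contains no fixed early dose window, no start of follow-up after titration, and no time-varying dose that would break the link.

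**Working it through.** **Planning distribution.** The plan gives no figure for this analysis, so the check uses its sample-size assumptions: control median 8.32 days and CV 1.0, taken as log-normal. The log-scale SD is √ln(1 + 1.0²) = 0.833. As a check on these inputs, n per arm = 2(1.960 + 1.282)² × 0.693 / (ln 1.6)² = 66. The plan states 65, where power is 0.896, so the inputs are close to those the plan used.

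**Average dose as a function of time to delivery.** Let T be days from first tablet to delivery and s the step length in days, with full tolerance and adherence. For T ≥ 2s, tablets taken = 2s + 4s + 6(T − 2s) = 6T − 6s, so the average is 6 − 6s/T tablets a day, which rises with T. Tablet strength is inferred as 3 g / 6 = 0.5 g. Protocol 4.3 prints the maximum in mg, which conflicts with 3 g and needs reconciling, but the artefact does not depend on the unit.

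| Delivery on day | 24 h steps: tablets/day (g/day) | 48 h steps: tablets/day (g/day) |
|---|---|---|
| 2 | 3.0 (1.50) | 2.0 (1.00) |
| 4 | 4.5 (2.25) | 3.0 (1.50) |
| 8.32 | 5.28 (2.64) | 4.56 (2.28) |
| 13.32 | 5.55 (2.77) | 5.10 (2.55) |
| 21 | 5.71 (2.86) | 5.43 (2.71) |

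(At day 2 with 48 h steps, T is below 2s and the woman is still on 2 tablets a day.)

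**Simulation with no drug effect.** There were 600 trials per setting, 75 per arm, with the same log-normal in both arms. Women were split at random between the two strata, gestational age was uniform within stratum, and prolongation was capped at 34 weeks. The model was a median regression of days on average dose (g/day) and stratum, with placebo dose 0.

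| Setting | p<0.05 favouring metformin | Mean slope, days per g/day |
|---|---|---|
| 4.3, 24 h steps | 24.3% | +0.71 |
| 4.3, 48 h steps | 66.5% | +1.43 |
| 4.3, steps 24–48 h, 25% of women capped at 1 or 2 g/day | 29.3% | +0.90 |
| 4.3, 24 h steps, all prolongations ≥ 2 days | 17.8% | +0.63 |
| 4.3, 48 h steps, all prolongations ≥ 2 days | 61.5% | +1.34 |
| 7.2.5, 25% halve the dose after a random day 1–4 | 1.3% (7.7% in either direction) | −0.21 |

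Under every 4.3 setting all significant results favoured metformin. Regression on randomised arm in the same trials rejected in 5.0–5.8%.

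Further simulations of the same kind gave 20% (24 h), 47% (mixed 24–48 h) and 63% (48 h), with 4–6% by arm. Under 7.2.5 they gave a slope of about −0.1 and 6% rejection. Another set with mixed steps gave 45%. That fell to 29% if 25% of women halve the dose at a random time between days 2 and 14, and to 22% if, in addition, 10% have a fetal demise and so a prolongation of zero.

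**Size in days.** At the average dose of a woman delivering at the planning median, the spurious effect is 0.71 × 2.64 = 1.9 days (24 h steps) or 1.43 × 2.28 = 3.3 days (48 h steps), against a target difference of 5 days.

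**The case against.** Four points can be made for the plan.

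- **The model is not written out.** Section 24 does not say that dose is continuous, that placebo is zero, or that dose replaces the arm term, and Analysis populations describes an arm comparison that would not have this bias. This stands as a limit on the size of the effect. It does not remove the problem, because section 24 carries the operative definition and the two descriptions cannot both be followed.
- **The direction depends on the dosing text.** A reader might infer that the analysis is biased towards benefit whatever happens. The documents do not support that. Under Protocol 7.2.5 early delivery leaves less time for a reduction, so the association is weak and negative. What is common to both texts is that average dose depends on time to delivery, under 7.2.5 only among women whose dose is reduced.
- **The upper figure is an extreme.** It needs every woman to take 48 hours at each step. Shorter steps, dose reductions and zero prolongation after fetal demise all weaken the effect. This stands, and the result should be read as a range.
- **It is only a sensitivity analysis.** A reader might infer that it could rescue a negative trial or open secondary testing. It cannot: the primary analysis is the stratum-adjusted intention-to-treat comparison, and SAP section 16 gates the secondary outcomes on that result alone.

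**Conclusion.** The concern holds, and the plan should be changed. As defined in SAP section 24(i), treatment received depends on the outcome. Under the Protocol 4.3 step-up, with dose as regressor and placebo coded zero, a trial of an inert drug would show a significant benefit in roughly 20% (24-hour steps) to 65% (48-hour steps) of cases, and less often if dose reductions are common. The nominal rate is 5%. These figures rest on the planning log-normal, on an inferred 0.5 g tablet, and on the assumed tolerance patterns stated above.

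The same simulations find a significant dose slope in nearly every null trial (99.7–100%) when only the metformin arm is analysed under the step-up. A reader might take that as the size of the problem. No passage plans such a regression; the metformin-arm dose measures in SAP section 19 are for description.

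The damage is confined to a misleading sensitivity analysis. The primary result and the secondary gate stand.

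**What to change.** 1. In SAP section 24(i), delete average daily dose as the exposure. Define treatment received as the product actually taken, metformin or placebo, compared by arm as Analysis populations already says, with the same stratum-adjusted median regression.
2. State how a woman who took no tablet is handled. She should not be moved into the placebo group, because SAP section 11 names delivery before any trial medication as one reason for taking none.
3. Keep average daily dose, and percentage of maximum dose, as descriptive adherence statistics only, as SAP section 19 already plans.
4. Reconcile the dosing descriptions in Protocol 4.3 and 7.2.5, and complete the broken sentence on escalation in SAP section 19.
5. If a dose-response is reported at all, label it exploratory. Use dose in a fixed early window among women undelivered at its end, with prolongation counted from that point.

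Items 1 to 3 cost SAP wording only. The by-arm version will probably differ little from intention to treat if few women receive the wrong product, so it says little about dose. Item 5 is optional and has a price. With a day-4 window, Φ((ln 4 − ln 8.32)/0.833) = 0.19, so about 19% of women would be lost under the planning assumptions, and confounding of dose by tolerance or disease severity would remain.

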#### Secondary aims:

- 2) To determine whether metformin can improve 1) maternal 2) fetal and 3) neonatal outcomes in early onset pre-eclampsia being managed expectantly compared to expectant management alone.
- 3) To examine whether metformin can significantly decrease levels of circulating sFlt-1 and/or sEng in women with early onset pre-eclampsia who are being managed expectantly compared to expectant management alone.
- 4) To examine whether metformin is safe and well tolerated in the mother and infant, compared with placebo.

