### 4.4 Sample size calculations

The primary research question is does treatment with metformin result in a gain in the median length of gestation of greater than or equal to 5 days compared to the mother receiving placebo therapy. This magnitude of prolongation we believe to be a clinically important difference and likely to have important beneficial implications for the fetus (although perinatal outcomes will not be a primary outcome in this phase II study).

Given the focus on median prolongation and the skewed nature of the gestation prolongation (seen in the two trials listed below) we based sample size calculations on the Geometric Mean Ratio (GMR). Analysis was performed both using PASS 13 (Power Analysis and Sample Size Software (2014). NCSS, LLC. Kaysville, Utah, USA, [ncss.com/software/pass](http://ncss.com/software/pass)) and the Powercal program running in Stata v15 (Stata statistical software. 2017 Release 15. Stata Corp. College Station, TX: StataCorp LLC).

Power calculations settings were: 90% power, with two-sided alpha set at 0.05, control median prolongation of 8.3 days and clinically important prolongation of gestation of 5 days. The measure of variability used in this analysis is the Coefficient of Variation (CV) = (data SD)/ data Mean) in mothers treated with standard expectant management. We have two sources for gestational prolongation in pre-eclamptic mothers receiving expectant management after PE diagnosis both undertaken at the same hospital where we plan to run this trial (Tygerberg Hospital). The first was by Hall et al, who in the largest descriptive study on expectant management of early onset pre-eclampsia reported a mean gestation prolongation of 11 (SD 7) days equivalent to a CV = 0.64. The second was the PIE trial, performed by [name] et al, where patients randomized to the placebo arm had an overall mean prolongation of 13.1 (SD 12.2) days, a CV = 0.93. In this study mothers entering with greater than 29 week gestations the CV = 0.8. We have chosen to use a CV = 1.0, slightly larger than the 0.93 found in our PIE study, to allow for adequate power if greater variability in prolongation times occurs in PI2.

The results of sample size requirements for a limited range of GMR and two CVs are presented in table 1.

Table 1: Sample size calculation

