Detectable prolongation in median days*	Treated group Median	GMR	Number per group (CV = 1.0)	Number per group (CV = 0.93)	Number per group (CV = 0.80)
3.11	11.43	1.37	137	134	105
4	12.32	1.48	88	87	69
5	13.32	1.6	65	61	49

\*placebo group median = 8.32 days

Using a CV = 1.0, 65 patients are required per group. Allowing for 10 dropouts/group, we require 75 patients per arm..

The gestational age at diagnosis is likely to affect allowable length of pregnancy prolongation. For instance, those diagnosed at 31+6 will be delivered at 34 weeks (should they reach that gestation), as it is unit policy to deliver at that gestation. Thus, such patients will have a maximum length of pregnancy prolongation of 15 days. In contrast, those diagnosed at 28 could conceivably obtain many weeks of pregnancy prolongation (if the disease remains stabilised). Further it is possible that metformin efficacy may vary with gestational age at diagnosis.

To ensure treatment group allocation is balanced for this potential variable, we will stratify randomisation into strata based on gestational age.

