### **7.2.3 Route of administration, dosage regimen and treatment period**

Each participant will be given a treatment pack by the study nurse. A copy of the randomisation number (from the randomisation website) will be placed in the participants trial folder. The treatment pack will be labelled with the participants name and trial number. The treatment pack will contain treatment for 21 days. Treatment will then be taken twice daily until the pregnancy has ended. Trial drugs will be kept in the packaging they are provided in and will under no circumstances be used for other participants. The trial medication will be written up on the treatment chart and the chart will be signed by the nursing staff to confirm that the participant

has taken the medication and to confirm compliance. The research midwife will monitor the treatment chart to assure compliance. As a second compliance check the patient will be asked to return the empty packaging to the research midwife who will record the number of empty tablet containers at the time of delivery of the patient.

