Creatinine (mg/dL)	Mean (SD)			
Estimated Fetal weight (g)	Mean (SD)			
Fetal weight centile	Median [IQR]			
Absent flow on umbilical artery Doppler	n (%)			

Table 3: Severe adverse events (presented as number with percentages)		
	Metformin (n=)	Placebo (n=)
MATERNAL		
Maternal death		
Eclampsia		
Cerebral vascular event		
Posterior reversible encephalopathy syndrome		
Left ventricular failure		
Pulmonary oedema		
Severe renal impairment		
Blood loss of more than 1000mls		
Disseminated intravascular coagulation		
Liver haematoma or rupture		
FETAL/NEONATAL		

Intrauterine demise		
Fetal or neonatal congenital anomaly		
Neonatal death		
Necrotising enterocolitis		
Neonatal sepsis		
Intracranial haemorrhage		

Table 4: Side effects from medication (presented as number with percentages)		
	Metformin (n=)	Placebo (n=)
Nausea		
Vomiting		
Diarrhoea		
Headache		
Decreased tablets		
Stopped medication

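### Table 4 reports side effects as ever/never percentages with no counting window although treatment lasts to delivery; a first-7-days column would make the tolerability comparison nearly independent of prolongation (minor, cheap improvement)

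*SAP*

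**What the plan says.** Protocol section 3.1 lists a tolerability aim: "To examine whether metformin is safe and well tolerated in the mother and infant, compared with placebo". SAP Table 4, "Side effects from medication (presented as number with percentages", has six rows by arm: nausea, vomiting, diarrhoea, headache, decreased tablets and stopped medication. It gives no observation window, no days of treatment and no onset timing. SAP section 27 (Harms) deals only with serious adverse events, also as number and percentage, without testing. Days of therapy appear in the SAP only as the divisor of an adherence measure (section 19).

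On duration, protocol section 4.3 says "Treatment will continue until delivery" and section 7.2.3 says "Treatment will then be taken twice daily until the pregnancy has ended".

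Two passages bear on when symptoms arise. Protocol section 4.3 looks for side effects 24 to 48 hours after each dose step. Section 2.5.2.4 warns that some metformin reactions resemble pre-eclampsia, and protocol Table 3 lists headache and nausea or vomiting among the adverse conditions of the disease.

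**The concern.** An ever/never percentage rises with the time over which events can be counted. Here that time is planned to end at delivery, and the trial is designed to show that delivery comes later on metformin. A comparison of Table 4 percentages can therefore mix two questions: how often symptoms occur while a woman takes tablets, and how long she takes them. Tolerability is the first question. If metformin works as hoped, part of any excess in Table 4 could reflect longer exposure, in a trial whose positive result is meant to lead to a larger multicentre study (protocol section 14.2).

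**Working it through.** **1. The plan's own figure.** Protocol section 4.4 uses "90% power, with two-sided alpha set at 0.05", "control median prolongation of 8.3 days and clinically important prolongation of gestation of 5 days" ("placebo group median = 8.32 days" under its Table 1), and "We have chosen to use a CV = 1.0". For log-normal times, the log-scale SD is sqrt(ln(1 + 1.0²)) = sqrt(ln 2) = 0.833. Then n = 2 × (1.960 + 1.282)² × 0.693 / [ln(13.32/8.32)]² = 65.8, or 66 per group, against 65 stated. The log-normal model is therefore a fair stand-in for the plan's assumptions.

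**2. Extra exposure if the 5-day effect is real.**

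| Source in the plan | Placebo | Metformin | Ratio |
|---|---|---|---|
| Sample size table, median | 8.32 | 13.32 | 1.60 |
| SAP survival table, median | 9 | 14 | 1.56 |
| Descriptive study at the hospital, mean | 11 | 16 | 1.45 |
| Earlier esomeprazole trial, placebo mean | 13.1 | 18.1 | 1.38 |

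**3. Constant risk to delivery.** The documents give no side-effect rate, so placebo values of 20% and 40% are assumed. With the same daily hazard h in both arms, P(ever) = 1 − E[exp(−h·T)], where T is time to delivery. T is log-normal with medians 8.32 and 13.32 and CV 1.0. Entry is assumed uniform over 26 to 32 weeks, and T is cut off at 34 weeks, when expectant management usually ends. Mean T is then 10.8 and 15.6 days (ratio 1.44).

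| Placebo, ever | Metformin, ever (34-week cap) | Without cap |
|---|---|---|
| 20% | 27.4% | 28.9% |
| 40% | 51.7% | 52.8% |

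With the smallest exposure ratio (means 13.1 and 18.1, CV 0.93, no cap), a risk of 2% per day gives 21.2% against 27.4%, and 5% per day gives 41.6% against 50.5%.

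**4. Risk only in the first W days.** Now P(ever) = 1 − E[exp(−h·min(T, W))]. In the capped model, with h set to give 20% on placebo, metformin shows 20.4% for W = 3 and about 22% for W = 7.

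**5. Counting only the first 7 days.** With the constant risk of step 3, the 20% case becomes 12.1% against 13.4%. The remaining gap arises because more placebo women deliver before day 7.

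**6. Events per 100 treatment-days.** Take the 3-day case of step 4 and divide first events by mean treatment time. Placebo has 20% / 10.8 days = 1.86 per 100 days; metformin has 20.4% / 15.6 days = 1.31. That is 29% lower at identical risk. For the 7-day case it is about 24% lower.

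**The case against.** The strongest objection is that metformin's side effects may come early. The 24 to 48 hour checks in protocol section 4.3 suggest this, as does section 7.2.5, which starts at six tablets and reduces for side effects. Those two passages disagree on the starting dose and must be reconciled, but both expect side effects soon after tablets begin or increase. Step 4 shows that the excess then nearly disappears. This stands for drug effects such as diarrhoea. It does not cover the whole table: background headache, nausea and vomiting can arise on any undelivered day, and tablet counts can be lowered and raised later. The heading does limit the table to side effects from medication, so some disease symptoms may not be counted. How many is not stated.

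Impact is also limited. Table 4 has no P-value column, the SAP sets no tolerability decision rule, and Table 2 shows prolongation by arm, so a reader can see the exposure difference. With 75 women per arm, the standard error of 20% against 27.4% is sqrt(0.20 × 0.80/75 + 0.274 × 0.726/75) = 6.9 points, so the artefact is about one standard error. Women who stop tablets early also have less exposure than their time to delivery.

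A reader might infer that Table 4 is bound to show more side effects on metformin, or that the SAP prescribes counting from first dose to delivery. The documents support neither. The 5-day gain is the alternative the trial is powered for, and the counting window is simply not stated.

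**Conclusion.** The gap is real but minor. Table 4 leaves its counting window open, and its percentages depend on time to delivery when two conditions hold together: gestation is prolonged, and risk persists. Under both, and under the capped log-normal model with assumed placebo percentages of 20% and 40%, the false excess is about 7 and 12 points. With risk confined to the first 3 to 7 days, the 20% case gains about 0.4 to 2 points. With no prolongation the excess is zero. The primary and composite analyses are untouched.

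A reader might also conclude that a rate per treatment-day is the cure. It is not a safe basis here: with early-onset effects it overcorrects by about 24-29%. The early fixed window is less sensitive to either pattern.

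**What to change.** Record the onset date of each side effect, and state in the SAP the window over which Table 4 counts. Add a column per arm with the number (%) who have each side effect, tablet reduction or stopping in the first 7 days of treatment. Women who deliver earlier should stay in the denominator, as in step 5. Base the between-arm tolerability statement on that column and keep the ever/never counts as description. Give total treatment-days per arm as context, but do not draw the conclusion from events per 100 treatment-days.

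The cost is a wider table, SAP wording and the onset dates. The dates are feasible to collect, because participants are inpatients with twice-daily clinical assessment and a signed treatment chart (protocol sections 7.2.3 and 7.3.1). The drawback is that later-onset effects appear only in the descriptive counts. No test, sample size or clinical care changes.
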